4. ANALYSIS SETS (POPULATIONS FOR ANALYSIS)

4.1. Safety Analysis Set

As the objective of the study is long-term safety and tolerability of ziprasidone, only one analysis set, “Safety Analysis Set” defined below will be used for data summaries.

The Safety Analysis Set (SAS) will include *all subjects who took at least one dose of study medication in this open-label extension study.*

All summaries will be based on the “as reported” visits (as recorded on the Case Report Forms).

For data summary purposes, subjects will be classified into one of the following two groups:

- Ziprasidone/Ziprasidone: randomized to ziprasidone in the preceding double-blind study (and on ziprasidone in the current open-label extension study).
- Placebo/Ziprasidone: randomized to placebo in the preceding double-blind study (and on ziprasidone in the current open-label extension study).

In addition, the above two groups will be combined as:

- Combined: combination of the two groups Ziprasidone/Ziprasidone and Placebo/Ziprasidone. This is essentially the set of all subjects in the current open-label extension study.

Data summaries will be done based on Ziprasidone/Ziprasidone and Placebo/Ziprasidone, as well as Combined.

4.2. Treatment Misallocations

If a subject took incorrect treatment in the preceding double blind study, then the subject will be reported under the treatment they actually received. For example, if a subject randomized to placebo but took Ziprasidone instead in the preceding double-blind study, then the subject will be reported under “Ziprasidone/Ziprasidone” rather than “Placebo/Ziprasidone”.

4.3. Protocol Deviations/Violations

A full list of clinically important protocol deviations/violations will be included in the Clinical Study Report. Note that protocol deviations/violations will not exclude subjects from the “Safety Analysis Set” defined in [Section 5.1](#).

5. GENERAL METHODOLOGY AND CONVENTIONS

5.1. Hypotheses and Decision Rules

As this is an open-label study with no comparator, no formal statistical hypothesis testing will be conducted.

5.2. General Methods

As this is an open label study with no comparator, no inferential statistics will be performed. Quantitative variables will be described by standard descriptive statistics (n, mean, standard deviation, minimum, and maximum, 95% confidence intervals), and qualitative variables will be summarized by frequency tables. Summaries will include data for all subjects who took at least one dose of investigational product in this open label extension study.

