6.2. Baseline Summaries

All demographic, baseline characteristics and pre-treatment conditions will be summarized using the safety population. Descriptive statistics, including number of patients, mean, standard error, median, and range for continuous variables, and frequency and percent for categorical variables, will be provided for all demographic, baseline characteristics, and pre-treatment conditions.

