6.5.1. Adverse Events

All randomized subjects who receive at least one dose of antipsychotic treatment will be included in the safety data summarization. All treatment emergent adverse events that are observed from the time of first dosing with open label investigational product until the end of study participation will be included in data summaries. All causality discontinuations and treatment emergent discontinuations from the study will be summarized.

An adverse event is considered treatment emergent relative to a given treatment if:

- the event occurs for the first time during the time of first dosing with open label investigational product until the end of study participation and was not seen prior to the start of treatment in open-label extension (for example, during the baseline or double-blind study), or

- the event was seen prior to the start of treatment but increased in severity during treatment.

All adverse events will be coded according to the Medical Dictionary for Regulatory Activities. The incidence of treatment emergent adverse events will be tabulated by system organ class. The incidence of treatment emergent adverse events will be displayed by severity and attribution. In addition, the incidence of serious adverse events and adverse events that cause withdrawal will be tabulated. All adverse events will be listed.

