6.5.2. Laboratory Data

All clinical laboratory data will be displayed in listings grouped by type of laboratory test (eg, hematology, blood chemistry) for each sample collection date. Values outside of the normal range will be noted; the respective normal high or low value will be presented in parentheses, linked to the abnormal laboratory value. Laboratory values will be summarized as median changes from baseline and also by frequency of occurrence of clinically significant abnormal values.

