6.5.6. Electrocardiograms

Centrally read ECG variables will be summarized by mean change from baseline to each measurement time for heart rate, PR interval, RR interval, QRS width, QT interval and QTcB (Bazett's correction) and QTcF (Fridericia's correction) values. Additionally, the incidence of categorical increases in QTc intervals will be provided. Categories for QTcF and QTcB are ≥ 450 msec, ≥ 480 msec, and ≥ 500 msec. Categories for QTcF and QTcB as change from baseline are ≥ 30 msec increase, ≥ 60 msec increase and ≥ 75 msec increase. QTcF is considered the primary QTc value as this correction is more appropriate.

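### The plan gives 95% confidence intervals to quantitative variables but none to the safety incidences, and SAP 6.2 names standard error where SAP 5.2 and protocol section 9 name standard deviation

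*SAP*

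**What the plan says.** SAP 5.2 sets the general rule, and protocol section 9 has the same text. For continuous data: "Quantitative variables will be described by standard descriptive statistics (n, mean, standard deviation, minimum, and maximum, 95% confidence intervals". For the rest: "qualitative variables will be summarized by frequency tables". An interval is named in the first half of the rule and not in the second.

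The sections on individual outcomes do not fill the gap:

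- SAP 6.5.1: "The incidence of treatment emergent adverse events will be tabulated by system organ class", and "the incidence of serious adverse events and adverse events that cause withdrawal will be tabulated".
- SAP 6.5.2: "Laboratory values will be summarized as median changes from baseline and also by frequency of occurrence of clinically significant abnormal values".
- SAP 6.5.4 asks for frequency tables of BMI z-score shifts.
- SAP 6.5.6: "the incidence of categorical increases in QTc intervals will be provided".

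None of these names an interval for a proportion.

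SAP 4.1 reports everything on one Safety Analysis Set (everyone dosed in the extension), for two prior-treatment groups and Combined. SAP 6.6 adds a subgroup from Chinese sites. SAP 2.1 and protocol 9.1 expect about 55 entrants.

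For the baseline table, SAP 6.2 departs from the general rule: "Descriptive statistics, including number of patients, mean, standard error, median, and range for continuous variables". Standard deviation is not in that list.

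**The concern.** The only objective is long-term safety and tolerability. Much of the answer will be counts: how many subjects had a serious event, withdrew because of an event, or crossed a QTc threshold. With about 55 subjects, and fewer in each reporting group, many of these counts will probably be zero or close to it. A table cell showing no events does not tell the reader how high the true rate could still be. The plan supplies an interval for the mean of a rating scale but not for the rate of serious adverse events.

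The results are meant to be used. SAP section 2 ties the study to a paediatric regulatory commitment, and SAP 6.6 says the China subgroup will support a submission. The smallest group is therefore one in which a zero is likely to be looked at closely.

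The baseline point is different in kind. A standard error describes how precisely a mean is estimated. A baseline table is there to describe how varied the subjects are, for which the standard deviation is the relevant figure. SAP 5.2 and SAP 6.2 also leave the programmer with two lists that do not agree.

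**Working it through.** **Is there a precision figure to reproduce?** No. Protocol 9.1 sets the sample size by rollover from the preceding study and states no precision target. Its only figures are about 55 entrants, about 35% dropout and about 40 completers. The arithmetic gives 55 × 0.65 = 35.75, not 40. That mismatch is a separate matter and is not used here, because SAP 4.1 makes everyone dosed the denominator, not completers.

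**Inputs**

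- n = 55: SAP 2.1 and protocol 9.1, if all eligible subjects enter.
- n = 28: assumed half split of 55. The documents give no split between prior-treatment groups.
- n = 18: assumed smaller group under an uneven split.
- n = 10 to 20: assumed China subgroup. SAP 6.6 gives no size.

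**Interval for an incidence.** Two-sided exact (Clopper-Pearson) 95% limits for x events in n subjects:

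- lower = 2.5% quantile of Beta(x, n − x + 1), and 0 when x = 0;
- upper = 97.5% quantile of Beta(x + 1, n − x). When x = 0 this is 1 − 0.025^(1/n).

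For 0 of 55: 1 − 0.025^(1/55) = 6.5%. For 0 of 28: 1 − 0.025^(1/28) = 12.3%.

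| Events / n | Observed | Two-sided exact 95% interval |
|---|---|---|
| 0 / 55 | 0% | 0 to 6.5% |
| 1 / 55 | 1.8% | 0.05 to 9.7% |
| 3 / 55 | 5.5% | 1.1 to 15.1% |
| 6 / 55 | 10.9% | 4.1 to 22.2% |
| 11 / 55 | 20.0% | 10.4 to 33.0% |
| 0 / 28 (assumed) | 0% | 0 to 12.3% |
| 0 / 18 (assumed) | 0% | 0 to 18.5% |
| 0 / 20 (assumed) | 0% | 0 to 17% |
| 0 / 10 (assumed) | 0% | 0 to 31% |

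The convention matters: a one-sided 95% bound for 0 of 55 is 1 − 0.05^(1/55) = 5.3%, so any statement of the limit has to say which is meant.

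**Chance of seeing no case at all in 55 subjects**, (1 − p)^55: 0.58 for a true rate p of 1%, 0.33 for 2%, and 0.06 for 5%. A zero count is quite compatible with a rate of 1% or 2%.

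**Standard error against standard deviation.** SE = SD / √n, so the SE is smaller by √n: 7.4 at n = 55 (Combined), 5.3 at n = 28, and 4.2 at n = 18.

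**The case against.** The strongest defence is that the study is descriptive by design. Protocol section 9 and SAP 5.1, 5.2 and 6 rule out hypothesis tests and inferential statistics, and the number of subjects is whoever rolls over. Incidence tables fit that plan, and a reader can rebuild an interval from x and n. This stands as far as it goes: nothing is miscalculated and no decision rests on the missing intervals. It does not explain the asymmetry, because the same paragraph that disclaims inference goes on to prescribe 95% intervals for quantitative variables. The plan already treats an interval as description.

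On the baseline table, the list in SAP 6.2 is introduced as non-exhaustive and can be read as adding to SAP 5.2. The number of patients, median and range are printed, and SD = SE × √n can be recovered. This also stands in part: spread is not hidden. The conflict in wording remains.

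A reader might infer more than the documents support:

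- That precision and spread will both be misread. Precision of the incidences is unreported, not misreported, and no section treats a zero count as proof of absence. What can be said is that a zero can be over-read.
- That incidences carry most of the safety result. That is a judgement. Blood pressure, weight, ECG changes, the movement scales and the depression scale are continuous or scored measures.
- That the baseline table will make subjects look several times more alike than they are. With the range printed beside the standard error, this does not follow.

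SAP 5.2 also does not say that its intervals are for means; that is only the natural reading.

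**Conclusion.** The point holds as a gap in reporting. The general rule and every outcome section leave the safety incidences without an interval, in a safety study of about 55 subjects. The size is clear for the Combined group: no events in 55 still allows a true rate of up to 6.5% (upper end of a two-sided exact 95% interval). In half the cohort the figure is 12.3%, which rests on an assumed even split. The range of 17% to 31% for the China subgroup rests on an assumed 10 to 20 subjects. The figure of 55 also presumes that all eligible subjects enter; with fewer, the limits are wider.

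The standard error in SAP 6.2 is a genuine but small inconsistency with SAP 5.2 and protocol section 9. Neither point biases an estimate, changes an analysis set or affects a decision rule. The recommendation is a worthwhile, inexpensive improvement.

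**What to change.** - **SAP 5.2:** add two-sided exact (Clopper-Pearson) 95% confidence intervals, stated to be descriptive and unadjusted for multiplicity. Apply them to the incidence of serious adverse events, adverse events leading to withdrawal, possibly suicide-related adverse events, treatment-emergent events above a frequency threshold fixed in advance, and each QTcF category. Use the Safety Analysis Set, for each prior-treatment group, Combined and the China subgroup.
- **SAP 6.5.1:** name possibly suicide-related adverse events as an output. Protocol 9.3 includes them; SAP 6.5 does not mention them.
- **Protocol 9.1 (optional):** state that 0 events in 55 subjects gives a two-sided exact 95% upper limit of about 6.5%.
- **SAP 6.2:** replace standard error with standard deviation.

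The cost is SAP wording and a small addition to the table programs, with no new data and no change in conduct. The downside is somewhat larger tables with many wide intervals, which the frequency threshold keeps in check, and reassurance from low counts that looks less favourable.

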5.3. Methods to Manage Missing Data

For any efficacy or special assessment rating scale/subscale or special safety variables where there is a missing rating (item), that scale or subscale will be scored as missing. If the whole scale has a missing item but the subscale has no items missing, the total score for the scale will be scored as missing but the subscale score will be computed.

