7.3.2.4. Columbia Suicide Severity Rating Scale (C-SSRS)

The Columbia Suicide Severity Rating Scale (C-SSRS)¹⁶ will be used to evaluate suicide ideation and severity at screening, baseline, and each post baseline visit. The C-SSRS is a semi structured interview that captures the occurrence, severity, and frequency of suicide related thoughts and behaviors during the assessment period. The interview includes definitions and suggested questions to solicit the type of information needed to determine if a suicide related thought or behavior occurred. The C-SSRS is the prospective counterpart to the Columbia Classification Algorithm of Suicide Assessment (C-CASA) categorization system.¹⁷ Responses to individual C-SSRS items can be mapped directly to the C-CASA categories (ie, completed suicide, attempted suicide, preparatory acts, suicidal ideation, non-suicidal, self-injurious behavior) for summary and analysis purposes. The C-SSRS has been broadly used in numerous industry sponsored randomized clinical trials (RCTs) in both Central nervous system (CNS) and non CNS indications.

The C-SSRS is available in a Baseline version and a “Since Last Visit” version. The baseline version assesses suicidal behavior over the lifetime and suicidal ideation at the time the subject was most suicidal. The “Since Last Visit” version assesses suicidal ideation and behavior between visits in a clinical trial. The clinician administering the interview should use information provided by the subject as well as other sources of information (eg, from parent(s) or guardian(s)) to determine if suicidal ideation or behavior occurred.

The C-SSRS contains 2 required items pertaining to suicidal ideation, 4 required items pertaining to suicidal behavior, and 1 required item pertaining to non-suicidal self-injurious behavior. There are 8 additional suicidal ideation items and 2 additional suicidal behavior items which are completed in cases of positive responses for other items, as well as 2 items for completed suicide and suicide behavior present during the interview. Thus, there is a maximum of 19 completed items.

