3.2. Special Safety Endpoints

- *Child Depression Rating Scale - Revised (CDRS-R).*
- *Columbia Suicide Severity Rating Scale (C-SSRS).*
- *Movement Disorder Scales (SARS, BAS, and AIMS).*

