6.4. Special Safety Analyses

No formal analyses for special safety assessments will be performed for this study. However data on the C-SSRS, CDRS-R and Movement disorder scales (SARS, BAS, AIMS) will be summarized using descriptive statistics as described above.

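### The SAP's missing-item rule covers the C-SSRS without exemption and, applied at scale or subscale level, can drop a recorded 'yes' because another item is blank

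*SAP*

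**What the plan says.** SAP 5.3 has one missing-item rule. For efficacy scales and "special safety variables where there is a missing rating (item), that scale or subscale will be scored as missing". Its second sentence protects a complete subscale inside an incomplete scale: "the total score for the scale will be scored as missing but the subscale score will be computed".

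SAP 3.2 lists the C-SSRS among the special safety endpoints, so the rule reaches it. SAP 6.4 adds only that "data on the C-SSRS, CDRS-R and Movement disorder scales (SARS, BAS, AIMS) will be summarized using descriptive statistics as described above". It defines no positive, no category and no subject-level count, and it does not treat the C-SSRS differently from the summed scales beside it.

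Protocol 7.3.2.4 describes a gated instrument. Seven items are asked of everyone: two on ideation, four on behavior and one on self-injury without suicidal intent. Of most of the others it says: "There are 8 additional suicidal ideation items and 2 additional suicidal behavior items which are completed in cases of positive responses for other items". Two more, on completed suicide and on behavior seen at the interview itself, bring the stated maximum to 19. The ideation, behavior and self-injury items are answered yes or no, and no total is formed except for Intensity of Ideation. The same section says that item responses can be mapped to C-CASA categories for summary. Protocol Section 2 places the C-SSRS in the primary endpoint column.

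**The concern.** An all-items-or-missing rule is sensible for a sum such as the YMRS, CDRS-R or SARS total, where a blank item leaves the sum undefined. It does not suit a set of yes/no items in which a single 'yes' already settles the question. If a subject reports suicidal ideation and the rater leaves another item of that block blank, the answer to whether ideation occurred is known, yet SAP 5.3 as worded would score the block as missing.

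The losses would not fall evenly. A positive answer opens further items, so the form of a subject with suicidality has more places where a blank can occur. The subjects most likely to be set to missing are those who should be counted. At stake is the suicidality result in a pediatric safety study, where few events are likely and each one matters.

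**Working it through.** **Step 1. Item count (protocol 7.3.2.4).** Required: 2 + 4 + 1 = 7. Not listed as required: 8 + 2 + 2 = 12. Total: 7 + 12 = 19, which reproduces the stated maximum. By block, ideation has 2 required and up to 2 + 8 = 10 items. Behavior has 4 required and up to 4 + 2 = 6. Self-injury has 1.

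The protocol also names five intensity ratings and calls them a subscale of their own. If those five are among the 8 additional ideation items, which is an inference, the yes/no ideation block has at most 10 − 5 = 5 items. Both sizes are carried below.

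**Step 2. Does the rule reach these blocks?** SAP 5.3 acts on a scale or subscale. Protocol 4.2 and 6.4 both call the ideation items a subscale of the C-SSRS. The provision for complete subscales does not help, because the blank lies inside the same subscale as the 'yes'.

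**Step 3. Chance of losing a recorded 'yes'.** Take the lenient reading, in which items properly not asked are not missing. Let m be the chance that an applicable item is left blank, independent across items. The documents give no value, so m = 0.5%, 1% and 2% are assumptions. A recorded 'yes' is lost if any of the j other applicable items in the block is blank:

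P(lost) = 1 − (1 − m)^j

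| Block and subject | j | m = 0.5% | m = 1% | m = 2% |
|---|---|---|---|---|
| Ideation, 'yes', all 10 items opened | 9 | 4.4% | 8.6% | 16.6% |
| Ideation, 'yes', 5 yes/no items only | 4 | 2.0% | 3.9% | 7.8% |
| Behavior, 'yes', all 6 items opened | 5 | 2.5% | 4.9% | 9.6% |
| One flag over the whole scale, 'yes', all 19 items opened | 18 | 8.6% | 16.5% | 30.5% |

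These are upper values for each block, because a 'yes' need not open every additional item.

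**Step 4. Comparison with subjects without suicidality.** Such a subject has only the required items, so the block is set to missing with probability 1 − (1 − m)^2 for ideation and 1 − (1 − m)^4 for behavior. At m = 1% these are 2.0% and 3.9%, against up to 8.6% and 4.9% for a subject with a 'yes'. The count of positives can only fall. The ideation proportion also falls once a 'yes' opens at least two further items (j of 3 or more, against 2 for a negative form).

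**Step 5. Scale of one loss.** With about 55 entrants (SAP 2.1), one lost positive moves a proportion by 1/55 = 1.8 percentage points. If 10% of 55, about 6 subjects, had ideation at one assessment (an assumed rate), the expected loss at m = 1% is 6 × 0.086 = 0.5 subjects with j = 9, or 6 × 0.039 = 0.2 with j = 4.

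**Step 6. Item-level or C-CASA tabulation.** Each 'yes' is then counted on its own item, there is no block score to set to missing, and none is lost. The rule would affect only the Intensity of Ideation total, where it is appropriate.

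**The case against.** The strongest reply is that SAP 5.3 is about scoring, and the C-SSRS is mostly not scored. Only Intensity of Ideation has a total, SAP 5.2 sends qualitative variables to frequency tables, and protocol 7.3.2.4 foresees mapping individual items to C-CASA. A programmer working that way would lose nothing. This stands as a limit on the claim: an error is possible, not certain. It does not remove the point. SAP 5.3 expressly names special safety variables and subscales, the protocol uses the word subscale for ideation, and the C-CASA mapping is not carried into the SAP.

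A second reply is that suicidality is also captured elsewhere. Protocol 9.3 includes possibly suicide-related adverse events, all adverse events are listed, and imminent suicide risk or repeated C-SSRS positives lead to withdrawal, with reasons tabulated under SAP 6.1. SAP 5.3 affects none of these, so a signal would not vanish from the study. They do not replace a C-SSRS table, however. The SAP plans no separate summary of suicide-related adverse events, and its treatment-emergent definition leaves out events seen earlier unless they worsened.

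A reader might go further and infer that the rule removes every subject without suicidality from the denominator, since such a subject can have up to 12 of 19 items uncompleted. The documents do not support that. It requires an item properly not asked to count as a missing rating, which the SAP does not say and which the protocol's split between required and additional items speaks against. On the ordinary reading, no subject with all required items answered is lost. The SAP is silent on the matter, so it should be closed in the same edit.

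**Conclusion.** The point holds as a defect in a stated rule. SAP 5.3 applies to the C-SSRS without exemption, does not fit a gated yes/no instrument, and at scale or subscale level permits a recorded 'yes' to be set to missing because of another blank item. The error would lower the suicidality count.

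Its size depends on a blank-item rate that the documents do not give. For assumed rates of 0.5% to 2% per item, independent across items, the chance of losing an ideation 'yes' at one assessment runs from 2.0% (5-item block, 0.5%) to 16.6% (10-item block, 2%), assuming all items of the block are opened. In a study of about 55 subjects that could mean one event or none. Whether any loss occurs depends on how the tables are programmed. The documents do not support saying that the suicidality result will be wrong. They do support saying that the SAP leaves it open to an avoidable error on an endpoint listed as primary.

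**What to change.** In SAP 5.3, add that the missing-item rule does not apply to the C-SSRS yes/no items, though it may stay for the Intensity of Ideation total. Then state three scoring rules:

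- Any recorded 'yes' counts as positive, whatever else is blank.
- An item not asked because its gate item was 'no' counts as 'no', not as missing.
- A category is missing only if a required item is blank and no 'yes' is recorded.

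In SAP 6.4, specify that the C-SSRS is tabulated by the C-CASA categories named in protocol 7.3.2.4, with each subject counted once over the extension, in addition to by-visit counts.

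The cost is a few sentences in the SAP and one extra table. No new data and no change to the visit schedule or the form are needed. The change should be made before the analysis is programmed.
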